16.5 Statistical Analysis

Demographics and baseline disease and treatment characteristics will be summarized using descriptive statistics such as counts and percentages, mean, standard deviation, median and range, as appropriate. This will include age, sex, race/ethnicity, performance status, prior systemic therapy, laboratory parameters (bone marrow function, liver function, etc.), and disease characteristics such as site (visceral, non-visceral), Child-Pugh classification and stage.

The number of Pembrolizumab injections received and reasons for treatment discontinuation will be summarized descriptively. Safety data, including toxicities, reasons for withdrawal from study treatment and laboratory data will also be summarized descriptively. Toxicities will be tabulated by type, grade, duration and attribution to treatment. A patient-level summary by worst grade toxicity will be included.

Efficacy analysis will include the primary study endpoint disease control rate (DCR), as well as the secondary endpoints, which include objective response rate (CR+PR), progression-free survival and overall survival. Disease control rate and overall response rate will be estimated by the percentage of patients achieving these criteria and the corresponding 95% confidence interval using the exact binomial method [40].

In addition, we will report median and range for the time to onset and duration of response for patients who achieve CR or PR. For patients whose best response is SD, we will report the median and range of SD duration.

The Kaplan-Meier method will be used to estimate progression-free and overall survival rates and corresponding median times, if attained. Point estimates with corresponding 95% confidence intervals based on Greenwood's variance and the log-log transform method will be given for the proportion of progression-free/surviving patients at selected times, such as 3, 6, 12, 18, and 24 months following the initiation of treatment, as well as for median times, if attained [41]. For purposes of these analyses, progression-free survival will be measured from start date of treatment to date of documented disease progression, or death from any cause, whichever occurs first. Patients who are alive and progression-free will be censored at their date of last documented progression-free status. Overall survival will be measured from start date of treatment to date of death from any cause. Patients who are alive will be censored at their date of last contact. To the extent possible with 28 patients, we will explore the effect of baseline characteristics on progression-free and overall survival using Cox regression [42]. The objective response rate (ORR) will be estimated by the percentage of patients and corresponding 95% confidence interval using the exact binomial method.

To the extent that biomarker data are available, we will summarize expression levels of PD-L- 1 in tumor tissue, and serum titers of hepatitis B and/ hepatitis C in patients with hepatitis B or C, respectively, using descriptive statistics. A descriptive analysis will be done for hypothesis-generating purposes but a statistical analysis will not be done as there may not be enough tumor tissue and blood samples collected (to conduct a formal statistical analysis).

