16.2 Study Design and Sample Size Justification

The primary endpoint for this single arm phase II trial is disease control rate (CR, PR, or SD). The rationale for using disease control rate (DCR) as the primary endpoint is derived from the clinical experience with Sorafenib (SHARP trial 2008), which was approved as the first and only therapeutic agent definitively proven to prolong survival in patients with advanced HCC. The disease control rate of Sorafenib was 43% in the SHARP trial [7]. We hypothesize that Pembrolizumab will achieve a similar or higher disease control rate. We set a null hypothesis rate of 18% disease control, since standard chemotherapy regimens generally result in a DCR of 15-20%.

We propose study size based on the Simon 2-stage MiniMax design [39] with a one-sided significance level of 5% and 90% power. Assuming that Pembrolizumab therapy will not be of further interest if DCR were no better than 18% (null hypothesis) while a rate of 43% would merit further investigation, the Simon MiniMax design requires at most 28 patients: 14 patients to be enrolled in the first stage and possibly an additional 14 in the second stage. If no more than 2 of the 14 patients in stage 1 achieve CR/PR/SD, the trial will stop and Pembrolizumab will be considered ineffective. If 3 or more of the stage 1 patients achieve CR/PR/SD, our study will continue to a second stage and enroll an additional 14 patients for a total of 28. If 9 or more out of 28 study patients achieve CR/PR/SD, we will report an observed DCR of at least 32% and conclude that the true DCR significantly exceeds a null rate of 18%. With this design, the chance of early stopping at the end of stage 1 is 53% if the null hypothesis of 18% DCR is true, whereas there is a very small chance, 2%, of early termination if the true DCR is 43%.

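### The only interval planned for DCR (95% exact binomial) does not match the two-stage one-sided 5% test, so a success at exactly 9/28 would be reported beside an interval that includes the 18% null

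*Combined protocol and SAP*

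**What the plan says.** Section 16.2 specifies a Simon minimax design "with a one-sided significance level of 5% and 90% power". The null is 18% ("We set a null hypothesis rate of 18% disease control"), and the rate of interest is 43%. The stages are 14 and 14: "If no more than 2 of the 14 patients in stage 1 achieve CR/PR/SD, the trial will stop". The final rule is a count. With 9 or more of 28, the plan states, "we will report an observed DCR of at least 32% and conclude that the true DCR significantly exceeds a null rate of 18" (per cent).

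Section 16.5 gives the analysis of the primary endpoint. DCR and the response rate will be "estimated by the percentage of patients achieving these criteria and the corresponding 95% confidence interval using the exact binomial method". It names no one-sided or 90% level and no adjustment for the interim look, and it does not say how the interval relates to the decision in 16.2. Section 17.2.3 restates the stage-1 rule and does not mention estimation.

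**The concern.** The test and the interval differ in two ways. The test puts 5% in one tail, while a two-sided 95% interval puts 2.5% in each. The test uses the two-stage sampling distribution, while the interval treats the final count as one binomial sample.

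Both differences matter at the smallest success that the plan itself names. The report would say that DCR is significantly above 18% next to an interval reaching below 18%. If the choice of a better-matched interval is left until 9/28 has been seen, it is data-driven and could be made to favour either impression. The raw percentage also ignores the stopping rule and so carries some bias.

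**Working it through.** **Inputs (all from 16.2 and 16.5).** n1 = 14, stop if X1 ≤ 2; n = 28, success if S ≥ 9; p0 = 0.18, p1 = 0.43; one-sided 5%, power 90%; planned interval 95% exact binomial.

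**Step 1: reproduce the design.**
- Early stopping: P(X1 ≤ 2 | 14, p) = 0.526 at 18% and 0.024 at 43%. The plan states 53% and 2%.
- Rejection: R(p) = Σ over x = 3 to 14 of P(X1 = x) · P(X2 ≥ 9 − x), with X1 and X2 each Binomial(14, p). R(0.18) = 0.0495 and R(0.43) = 0.905.
- A search finds no qualifying design with n from 24 to 27, and 14/2, 28/8 has the smallest expected sample size under the null at n = 28. The stated design is confirmed.

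**Step 2: the planned interval.** The Clopper-Pearson lower limit is the α/2 quantile of Beta(s, 29 − s); the upper limit is the 1 − α/2 quantile of Beta(s + 1, 28 − s).
- 9/28 (32.1%): 15.9% to 52.4%, includes 18%.
- 10/28 (35.7%): 18.6% to 55.9%, excludes 18%.

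So 9/28 is the only success count in conflict.

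**Step 3: which difference causes it.** Every final outcome of a trial that continued ranks above every stage-1 stop. The two-stage upper tail at 9/28 is therefore R(p), and the two-stage p-value is R(0.18) = 0.0495. The two-stage lower limit solves R(p) = tail level.

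| Interval at 9/28 | Limits | Excludes 18%? |
|---|---|---|
| Single-stage 95% (planned) | 15.9% to 52.4% | No |
| Single-stage 90% | 17.9% to 49.4% | No, narrowly |
| Two-stage 95% | 16.0% to 52.6% | No |
| Two-stage 90% | 18.04% to 49.6% | Yes |

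Changing the level moves the lower limit by about 2 points (15.9% to 17.9%). Changing to two-stage limits moves it by about 0.1 point (17.9% to 18.04%). The level is the main cause, but both changes are needed for agreement. The reason is that P(S ≥ 9 | 28, 0.18) in a single stage is 0.0514. Removing the 0.0020 chance of reaching 9 after 2 or fewer in stage 1 gives 0.0495.

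**Step 4: how often.** P(continue and S = 9) is 7.6% at a true DCR of 43%, 15.1% at 32% and 3.0% at 18%.

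**Step 5: coverage of the planned interval under the two-stage rule.** 98.0% at a true DCR of 18%, 97.1% at 25%, 98.0% at 32% and 94.8% at 43%.

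**Step 6: bias of the raw percentage, in points.**

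| True DCR | All trials | Trials reaching stage 2 |
|---|---|---|
| 18% | −2.1 | +4.4 |
| 32% | −1.2 | +1.4 |
| 43% | −0.4 | +0.4 |

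The uniformly minimum-variance unbiased estimate (UMVUE) at 9/28 is Σ C(13, x−1)·C(14, 9−x) ÷ Σ C(14, x)·C(14, 9−x) over x = 3 to 9. This is 2,172,456 ÷ 6,550,544 = 33.2%, against 32.1% raw.

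**The case against.** The strongest reply is that nothing here is in error. Section 16.2 fixes the decision by a count and states the conclusion to be drawn; 16.5 presents the interval as estimation and never as a test. Rejecting at one-sided 5% while failing to exclude 18% at 2.5% per side is two answers to two questions. Section 16.5 uses 95% intervals for DCR, the response rate and the survival endpoints alike, which is ordinary practice. Only one count is affected, and the interval's coverage is close to or above its label.

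Most of this stands. A reader might infer that the test is wrong, that success at 9/28 is not legitimate, or that the plan leaves the decision open. The documents support none of these: the count rule governs, and its exact error rate is below 5%. The single-stage p-value of 0.0514 belongs to an analysis that the plan does not propose. A reader might also infer that the raw percentage is simply too low. That holds only when averaged over all trials; among those that reach 28 patients it is too high.

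What survives is narrower. This is the only interval planned for the primary endpoint, it is not labelled descriptive, and at the plan's own threshold it appears to contradict the stated conclusion.

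**Conclusion.** The point holds as a mismatch between reporting and test, and its weight is modest. It is confined to 9/28, where the report would pair a significant result (p = 0.0495) with an interval of 15.9% to 52.4%. The design, alpha, power and futility rule are correct, and the 95% interval is a valid description. The bias in the raw figure is small at the boundary: 1.1 points below the unbiased estimate (33.2 − 32.1).

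Three assumptions carry this. First, the exact binomial method is taken to be single-stage Clopper-Pearson; that is the plain reading, but the supporting reference [40] cannot be checked because the reference list shown ends at 19. Second, exactly 14 + 14 patients are analysed. Section 16.4 allows up to 35 enrolled to secure at least 28 evaluable, and 16.3 defines the efficacy set more widely than 3.1.1, which also requires a post-baseline assessment, so the analysed number could differ. Third, coverage was checked only at 18%, 25%, 32% and 43%.

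**What to change.** In 16.5, for DCR, add:
- the two-stage p-value;
- the UMVUE beside the raw percentage;
- a two-sided 90% interval, whose lower end is the one-sided 95% bound, from the two-stage sampling distribution and computed for the stage sizes actually analysed.

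State that this interval accompanies the 16.2 decision. Keep the 95% exact interval as a labelled descriptive figure.

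The cost is SAP wording and a few lines of code; patients, data, sample size and decision rule are untouched. The downside is one more interval to explain. The agreement at 9/28 is by construction with 14 + 14, but the margin is thin (18.04% against 18%). If the analysed numbers differ, the p-value and limits must be recomputed, and agreement with the 9/28 rule is not guaranteed.

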17.0 DATA REPORTING

Data must be submitted according to the protocol requirements for all patients registered. Patients for whom documentation is inadequate to determine eligibility will generally be deemed ineligible.

17.1 Data and Safety Monitoring

The Sylvester Comprehensive Cancer Center (SCCC) Data and Safety Monitoring Committee (DSMC) will monitor this clinical trial according to the Cancer Center's DSM Plan. In its oversight capacity, the DSMC bears responsibility for suspending or terminating this study. DSMC oversight of the conduct of this trial includes ongoing review of accrual and adverse event (AE) data, and periodic review of the study therapy. The guidelines appearing in this section are offered for DSMC consideration in assessing AEs and response to study treatment. In addition, the DSMC will review reports from all audits, site visits, or study reviews pertaining to this clinical trial and take appropriate action. The SCCC DSM Plan to which this study is subject can also be found at www.sylvester.org.

17.2 Stopping Rules (for the study as a whole)

17.2.1 Early Stopping Guidelines

We propose the following guidelines for the DSMC in its review of accumulating data. For safety, we propose early stopping guidelines based on a Bayesian method. Early stopping guidelines for lack of efficacy are built into the Simon 2-stage design for this trial. Specific details are presented in the remainder of this section.

17.2.2 Safety: Early Stopping Due to Excessive Toxicity

We propose the following guidelines for the DSMC in its review of accumulating data on toxicity. The proposed guidelines were developed using Bayesian methods, which can be applied at any stage of enrollment without advance specification of the number of interim analyses to be performed, or the number of patients evaluable for toxicity, at the time such assessments are made [43-44].

Under the Bayesian method, we assign a prior probability (level of belief at the start of the trial) to a range of possible values for the true toxicity rate. As data on treated patients become available, each of these probability distributions is revised

and the resulting posterior probability becomes the basis for recommending either early termination or continuation of the study. Specific stopping guidelines and details on the prior distribution assumptions, and the resulting posterior probabilities are presented below.

For purposes of safety monitoring, we define an unacceptable toxicity to be any treatment-related (i.e., possible, probable, or definite) grade 3 or higher toxicity excepting nausea, reversible elevation of liver function tests and reversible myelosuppression. Prolonged (defined as ≥ 12 weeks,) grade 3 or higher elevation of liver function tests or myelosuppression will be considered unacceptable. Patients with hepatitis may take longer to recover their counts but it is considered justifiable given their poor prognosis. Early stopping (suspension and possibly termination) will be considered if there is evidence that the proportion of patients experiencing unacceptable toxicity exceeds 20%.

Specifically, we suggest as a guideline for early termination, a posterior probability of 90% or higher that the rate of unacceptable toxicity exceeds 20%. The table below shows specific instances where this guideline is met, thus suggesting early termination due to evidence of excessive toxicity.

For example, if 8 evaluable patients have been assessed for toxicity, the second row of the above table indicates that early stopping should be considered if 4 (or more) of these patients have experienced unacceptable toxicity. Note that 4 of 8 patients with unacceptable toxicity is an observed toxicity rate of 50%.

Posterior probabilities used to derive the preceding table are calculated under a prior beta distribution with parameters $\beta_1 = 0.4$ and $\beta_2 = 1.6$, which corresponds to an expected rate of 20% based on very limited information, roughly equivalent to having studied two patients. This prior distribution implies an a priori chance of 36% that the rate of unacceptable toxicity is 20% or greater.

Number of patients with unacceptable toxicity*	Total patients evaluated	Observed toxicity rate
3	4 to 6	$\geq 50\%$
4	7 to 10	$\geq 40\%$
5	11 to 13	$\geq 39\%$
6	14 to 17	$\geq 35\%$
7	18 to 21	$\geq 33\%$
8	22 to 25	$\geq 32\%$
9	26 to 27	$\geq 32\%$

*Possibly, probably or definitely treatment-related, grade 3+ toxicity excepting nausea, reversible elevation of liver function tests and reversible myelosuppression.

17.2.3 Early Stopping for Lack of Efficacy

The Simon two-stage design of this trial, described in Section 16.2, provides for a single interim analysis of the primary study endpoint, disease control rate (DCR).

After enrollment of the first 14 evaluable patients in stage 1, accrual will be suspended and a decision to terminate the study early or continue accrual will be made. DCR of this cohort of 14 evaluable patients from stage 1 will be determined as a best overall response of either a CR, PR, or SD (as detailed in section 14.5). If no more than 2 of the first 14 patients achieve DCR, the trial will stop and pembrolizumab will be considered ineffective, as this suggests that the DCR is no better than the null hypothesis rate of 18%. If DCR is achieved in 3 or more of the first 14 patients, the trial will continue to a second stage and enroll an additional 14 patients for a total evaluable number of 28 patients. The findings of interim analysis of DCR from the first 14 patients of stage 1 will be reported to the Sylvester DSMC.

17.2.4 No Early Stopping for Treatment Efficacy

We do not intend to stop the study early if the proposed study treatment appears to be effective. Under such circumstance, continuation of the trial will yield additional information regarding the magnitude of the true DCR. Moreover, if results from this study are promising, further studies will be needed to fully assess the benefits and risks of Pembrolizumab therapy in the treatment of patients with advanced unresectable hepatocellular carcinoma.

18.0 STUDY AUDITING AND MONITORING

This study will be audited and monitored according to <http://uresearch.miami.edu/regulatory-compliance-services/rcqa> and the Office of Research Integrity Assurance, respectively.

19.0 INVESTIGATOR RESPONSIBILITIES

19.1 Investigator Responsibility/Performance

The investigator will ensure that this study is conducted in accordance with all regulations governing the protection of human subjects. The investigator will ensure that all work and services described in or associated with this protocol will be conducted in accordance with the investigational plan, applicable regulations, and the highest standards of medical and clinical research practice.

19.2 Confidentiality

The investigator must ensure that each subject's anonymity will be maintained and each subject's identity will be protected from unauthorized parties. A number will be assigned to each subject upon study entry and the number and the subject's initials will be used to identify the subject for the duration of the study. The investigator will maintain all documents related to this study in strict confidence.

19.3 Informed Consent and Permission to Use Protected Health Information

It is the responsibility of the investigator to obtain written informed consent from each subject participating in this study after adequate explanation, in lay language, of the methods, objectives, anticipated benefits, and potential hazards of the study. The investigator must also explain that the subject is completely free to refuse to enter the study or to discontinue participation at any time (for any reason) and receive alternative conventional therapy as indicated. Prior to study participation, each subject will sign an IRB approved informed consent form and receive a copy of same (and information leaflet, if appropriate). For subjects not qualified or able to give legal consent, consent must be obtained from a parent, legal guardian, or custodian. The investigator or designee **must** explain to the subject before enrollment into the study that for evaluation of study results, the subject's protected health information obtained during the study may be shared with the study sponsor, regulatory agencies, and the IRB. It is the investigator's (or designee's) responsibility to obtain permission to use protected health information per HIPAA from each subject, or if appropriate, the subjects' parent or legal guardian.

19.4 Source Documentation and Investigator Files

The investigator must maintain adequate and accurate records to fully document the conduct of the study and to ensure that study data can be subsequently verified. These documents should be classified into two separate categories: (1) investigator study file and (2) subject clinical source documents that corroborate data collected on the CRF's. Subject clinical source documents may include hospital/clinic patient records; physician's and nurse's notes; appointment book; original laboratory, ECG, EEG, radiology, pathology, and special assessment reports; pharmacy dispensing records; subject diaries; signed informed consent forms; and consultant letters. When the CRF or any form is used as the source document, this must be clearly stated in the investigator study file. Minimally, the following be documented in source documents:

- Medical history/physical condition and diagnosis of the subject before involvement in the study sufficient to verify protocol entry criteria
- Study number, assigned subject number, and verification that written informed consent was obtained (each recorded in dated and signed notes on the day of entry into the study)
- Progress notes for each subject visit
- Documentation of treatment
- Laboratory test results
- Adverse events (action taken and resolution)
- Condition and response of subject upon completion of or early termination from the study

19.5 Recording and Processing of Data

If using hard copies of CRF's, study center personnel will complete individual CRF's in black ink. All corrections to entered data will be made by drawing a single line through

the information to be corrected without obscuring it. All corrections will be initialed, dated and explained, if necessary. The use of “white-out” or obscuring correction tape will be prohibited. A CRF is required for every patient who received any amount of study treatment. The investigator will ensure that the CRF’s are accurate, complete, legible and timely. Separate source records are required to support all CRF entries except those for which use of the CRF as source document is clearly allowed per note in the investigator study file.

Data must be submitted according to the protocol requirements for ALL patients registered. Patients for whom documentation is inadequate to determine eligibility will generally be deemed ineligible.

19.6 Non-Protocol Research

No investigative procedures other than those described in this protocol will be undertaken on the enrolled subjects without the agreement of the IRB.

19.7 Ethics

The investigator agrees to conduct the study in compliance with the protocol, current good clinical practices, and all applicable (local, FDA) regulatory guidelines and standard of ethics.

UM Ethics Programs’ Research Ethics Consultation Service (RECS) is a free resource for UM Researchers. See the website for further information:

<http://www.miami.edu/index.php/ethics/projects/recs/>

